10.2.2 Methods

English-speaking patients who consent will be given a packet of quality of life questionnaires to be completed in the clinic. The CRA will be available to answer any questions that the patients have, and review the questionnaires for completeness when handed in. If the questionnaires are not complete, patients will be asked if they left out answering the question by mistake or because they didn't wish to answer the question. If the former, patients will be asked to answer those questions; if the latter, patients will not be asked anything further. Patients will be assessed at baseline, 3, 5, 7, 12, 26, and 52 weeks

after the start of radiation therapy (see schedule outlined below). By 7 weeks, RT will have been completed for all arms of the study. The 12, 26, and 52 week assessments will allow us to examine the longer term effects of toxicity on patients' quality of life. The CRAs at the institutions will be called by the centralized CRA at the Psycho-Oncology Research Office at Dana-Farber Cancer Institute at each timepoint to remind them to administer the questionnaires to the patients. The schedule of assessments is outlined below:

- a) Baseline
- b) 3 weeks after the start of radiation therapy (completion of RT on 45 Gy, 1.5 Gy twice daily over 3 weeks. Mid-RT for 70 Gy once daily over 7 weeks; and 61.2 Gy, 1.8 Gy daily for 16 days, followed by 1.8 Gy twice daily for 9 days); cycle 2 chemotherapy [Cisplatin and Etoposide])
- c) 5 weeks after the start of radiation therapy (completion of 61.2 Gy; mid-treatment for 70 Gy); mid-cycle 2 chemotherapy [Cisplatin and Etoposide])
- d) 7 weeks after the start of radiation therapy (RT completed for all arms; cycle 3 chemotherapy [Cisplatin and Etoposide])
- e) 12 weeks after the start of radiation therapy (5 weeks post-completion of 70 Gy arm; 6.5 weeks post completion of 61.2 Gy arm; 9 weeks post-completion of 45 Gy. Completion of chemotherapy (Cisplatin and Etoposide])
- f) 26 weeks after the start of radiation therapy to assess longer-term consequences of patients' radiotherapy treatment on their quality of life
- g) 52 weeks after the start of radiation therapy to assess long-term consequences of patients' radiotherapy treatment on patient's quality of life
- h) Weekly during RT: ECOG Acute Esophagitis Scale and Difficulty Swallowing Item

The FACT-L, the FACT Eating and Swallowing Subscales, and the HADS are the only patient-reported quality of life measures that are translated into Spanish. Therefore, the quality of life component will be restricted to English-speaking patients only.

10.2.3 Measures

The Quality of Life battery will include measures of lung cancer-related physical symptoms, esophagitis, physical functioning, psychological state, quality-adjusted life years, treatment inconvenience, and sociodemographic characteristics, all of which (with the exception of sociodemographic characteristics) are hypothesized as being sensitive to differences in the treatment arms (see the table in [Section 6.2](#)). Acute esophagitis toxicity ratings will be obtained from the oncologist; all other quality of life data will be obtained from patient-completed questionnaires which will take the patient approximately 25 minutes to complete (see the table in [Section 6.2](#) for the frequency of administering the different scales). Several measures that have been included in our study (FACT-Lung Cancer TOI, EQ-5D, difficulty swallowing item, all described below) are also being used in a radiation therapy trial in the RTOG (R0617) of 60 Gy versus 74 Gy in non-small cell lung cancer patients. This will create a large database by which to examine the effect of RT on the quality of life of both non-small cell and small cell lung cancer patients. The majority of patients in the study will have prophylactic cranial irradiation (PCI). The effect of PCI on quality of life measures is not clear. In the meta-analysis of PCI for limited stage small cell lung cancer [63] neuropsychological evaluation was performed in two trials [64, 65]. The initial neuropsychological assessment, performed in 350 patients, revealed that many patients had abnormalities prior to PCI. The results of repeated tests during the first years of follow-up revealed that the changes in neuropsychological function and the frequency of abnormalities

on CT scans of the brain did not differ between the treated and untreated patients. Consequently, an in-depth neuropsychological assessment of patients and the potential impact of cognitive deficits on physical functioning and psychological state were not deemed necessary. Moreover, the primary Quality of Life endpoints are determined prior to PCI administration. Whether patients received PCI will be noted in the analyses of secondary endpoints that occur in the follow-up period after completion of all therapy.

- ECOG Acute Esophagitis Toxicity Criteria (C-1733)

The ECOG Acute Esophagitis Criteria consist of 4 items involving patients' assessment of sore throat/dysphagia, analgesics required, nutrition/hydration, and weight loss [58]. The scoring system integrates multiple objective and subjective criteria in the determination of an overall esophagitis grade. Using this point system, an ECOG grade 0 equals 0 points, grade 1 equals 1-3 points, grade 2 equals 4-6 points, grade 3 equals 7-9 points and grade 4, 10-12 points. This will be completed by the oncologist on a weekly basis while the patient is receiving RT in each of the arms, and then at all subsequent assessments.

- Difficulty Swallowing (Form C-1736)

At the time of each assessment, patients will report swallowing difficulties based on their response to the following item: "Have you had any problem with swallowing today?" The responses are made on the following 5-point scale: 1=none; 2=mild soreness; 3=can swallow solids with some difficulty; 4=cannot swallow solids; 5=cannot swallow solids or liquids. Time of assessment is less than a minute.

- FACT-Esophagus Eating and Swallowing Subscales (Form C-1734)

The FACT-Esophagus Subscale consists of 17 items that are specific to patients with esophageal cancer, including eating, appetite, swallowing, pain, talking/communicating, mouth dryness, breathing difficulty coughing and weight loss [66]. All items are rated on a 5-point Likert scale ranging from 0, "not at all," to 4, "very much." For purposes of this study, in which esophagitis is one of the primary symptoms of radiotherapy, the Eating and Swallowing subscales will be used. The Swallowing Index consists of 5 items, and the Eating Subscale consists of 3 items. Internal consistency of both subscales is excellent, with the Eating Index having alpha coefficients of .84-.88, and the Swallowing Index having alpha coefficients of .82-.86. Evidence for validity was found in that for patients in the neoadjuvant chemoradiotherapy group, there was a significant improvement in the Eating and Swallowing Indices from time in treatment to post-treatment completion. It takes approximately 2-3 minutes to complete the scales.

- Functional Assessment of Cancer Therapy Scale: Lung Cancer (FACT-L)
(Form C-1732)

The FACT-L [67] consists of the FACT-G [68] and the lung cancer subscale. The FACT-G (version 4.0), developed by Cella and colleagues [68] is an overall cancer-specific quality of life questionnaire. It is a 27-item core quality of life measure grouped into four subscales: physical well being, social/family well-being, emotional well-being, and functional well-being. The Lung Cancer subscale consists of 10 items, involving lung cancer-specific physical symptoms and regret about smoking. All items are rated on a 5-point Likert scale, ranging from 0, "not at all," to 4, "very much." The FACT-G has been tested on 545 patients with mixed cancer diagnoses. The internal consistency of the subscales ranges from moderate to excellent, from .65-.82, with excellent internal consistency of the total score, with an alpha coefficient of .89. Test-retest reliability is excellent within a 7-day period, with correlations ranging from .82-.92. Convergent validity has been demonstrated, with the FACT correlating significantly with other quality of life measures (FLIC, $r=.79$), and related constructs of psychological distress (e.g., Brief POMS, $r=-.68$), and the ECOG

performance rating ($r=-.52$) [68]. The FACT-G has been able to distinguish between patients with metastatic and non-metastatic disease. It has been determined that a 2 point difference on the FACT-G subscales and a 5 point difference on the FACT-G total score was associated with meaningful differences on clinical and subjective indicators [69]. In a review of the literature, Butt et al. [70] reported that the FACT-L scale has been used with more than 5,000 patients and been found to be sensitive to change in performance status over time, treatment response and correlate with dyspnea. The FACT-L is frequently used in clinical trials and studies of cancer patients' quality of life and is available in 20 foreign languages. The FACT-L will take approximately 10 minutes to complete.

The FACT-Lung Cancer (FACT-L) Trial Outcome Index (TOI) consists of the Physical Well-Being, Functional Well-Being and Additional Concerns (lung cancer-specific physical symptoms) subscales, for a total of 24 items [71]. It is a shortened version of the FACT-Lung Cancer Scale, which also includes Emotional and Social Well-Being. All items are rated on a 5-point Likert Scale, ranging from 0, "not at all," to 4, "very much." Evidence for validity of the FACT-L TOI was provided by finding that those with a significantly lower performance status had lower FACT-L TOI scores. Further, those patients with progressive disease had significantly lower TOI scores than those in the complete and partial responders groups. Last, those patients who progressed early had significantly larger negative declines in TOI scores than those who progressed later. Cella et al.'s [71] study has determined that a 5-7 point change in the FACT-Lung Cancer TOI is a clinically meaningful difference.

- Hospital Anxiety and Depression Scale (Form C-458)

The Hospital Anxiety and Depression Scale (HADS) [72] is a 14-item self-administered measure, which has been well tested in cancer populations. It has two 7-item subscales assessing depression and anxiety. The scale is considered particularly appropriate for use with medically ill patients because of the absence of somatic items, which often confound the determination of psychiatric problems in this population. Reported anxiety and depression cutoff scores on the HADS have varied from eight [73] to eleven [74]. The total cutoff score for psychological distress has ranged from 13, reflecting adjustment disorder, to 19, reflecting major depressive disorders [75]. Ibbotson and colleagues [76] found that for patients in active treatment, an overall cutoff score of 15 or greater resulted in 85% sensitivity, 77% specificity and a positive predictive value of 47%. For purposes of this study, 15 or greater on the HADS total score and 11 or greater on the HADS Anxiety and Depression subscales [74] will be used as the cutoff score indicative of a possible psychiatric disorder. The HADS will take approximately 8 minutes to complete.

- Subjective Significance Questionnaire (Form C-616)

In order to better interpret the clinical significance of changes in quality of life scores, Osoba et al. [77] developed the Subjective Significance Questionnaire (SSQ), consisting of 4 items in which patients rated the degree to which they saw an improvement in their physical condition, emotional state, ability to enjoy their social life and overall quality of life since their last quality of life assessment. All items are rated on a 7-point Likert scale, ranging from "very much worse" to "very much better," with each point on the scale anchored. The SSQ will be used to examine their scores in relation to corresponding changes in the FACT-L domains of quality of life. When used in relation to the EORTC QLQ C-30, increasing SSQ ratings were found to correspond with increasing EORTC scores in both breast and lung cancer patients, with small, moderate or large changes in quality of life defined in relation to changes in EORTC scores [78]. This will take 1 minute to complete.

- EQ-5D (Form C-903)

EQ-5D is a measure of health status for use in evaluating health and healthcare. It provides a simple descriptive profile of 5 functional dimensions and generates a single utility value for health status on which best imaginable health is assigned a value of 1 and worst imaginable health a value of 0. Thus, the index can be used to obtain a utility for these dimensions for use in economic analyses. The EQ-5D has been specially designed to complement other quality of life measures such as the SF-36, or cancer-specific measures. Descriptively, the EQ-5D consists of 5 dimensions, mobility, self-care, usual activity, pain/discomfort, and anxiety/depression. Each dimension has 3 levels designated simply as “no problem,” “some problem,” or “extreme problem,” with patients checking the level most descriptive of their current level of function on each dimension. Five dimensions, each with three levels, yield 243 possible distinct health states comprising the classification system. The classification system has been assigned different standardized scores derived through population-based samples of respondents who assign values to subsets of the 243 states using the anchoring labels noted above [79]. A set of valuation weights has thus been derived from a U.S. sample more recently [79, 80]. The Agency for Healthcare Research and Quality has funded a study to develop definitive weights. EQ-5D is designed for self-completion by patients and has been used extensively in mailed surveys. It is cognitively simple, taking no more than a few minutes to complete. Quality-adjusted life years can be calculated from using the EQ-5D in conjunction with a utility scale of health states.

- Treatment Inconvenience (Form C-1735)

The different treatment arms have different dose schedules for different lengths of times, which may impact the satisfaction with treatment due to the inconvenience posed. Therefore, an item will be added as to the inconvenience of going for therapy at the different dose schedules.

- Sociodemographic Characteristics (Form C-187)

Demographic data, including education, marital status, employment and household composition, will be obtained at baseline only using the CALGB Background Information Form [81] (CALGB Form C-187). Age, gender, and ethnicity will be obtained upon patients' registration to the study.

- QOL Assessment Form (Form C-419, revised)

In order to track data collection, and reasons for missing data, a QOL Assessment Summary Form will be completed for each patient by the CRA, for each assessment, coding whether the assessment was conducted and data collected, and if not, the reason why.

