5.5 Stratification

- Gender: male vs. female
- Weight loss (6 months prior to study entry): $\leq 5\%$ of body weight vs $> 5\%$ of body weight
- ECOG Performance Status: 0 vs 1 vs 2
- Planned Radiotherapy Technique: IMRT vs. 3D conformal
- Radiotherapy Start Time (choose 1, 2 or 3):

For patients receiving 1 cycle of non-protocol therapy prior to registration:

- 1) Start radiotherapy at the first cycle of protocol chemotherapy, after one cycle of prior non-protocol chemotherapy

For patients starting treatment right after registration (no non-protocol therapy):

- 2) Start radiotherapy at the first cycle of protocol chemotherapy, without prior non-protocol chemotherapy
- 3) Start radiotherapy at the second cycle of protocol chemotherapy, without prior non-protocol chemotherapy

- Chemotherapy backbone: carboplatin vs. cisplatin

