6.2 Data Submission for QOL

All participating institutions must ask patients for their consent to participate in the Quality of Life Studies in CALGB 30610 (CALGB 70702), although patient participation is optional. Patients registered to CALGB 30610 after they receive one cycle of chemotherapy will not participate in the QOL study. Rationale and methods for this study are described in [Section 10.2](#). For patients who consent to participate, assessments will be collected at the following time points:

Form		Baseline	Weekly during RT	Week 3*	Week 5*	Week 7*	Week 12*	Week 26*	Week 52*
(Assessment No.)		(#0)		(#3)	(#5)	(#7)	(#12)	(#26)	(#52)
C-1732	FACT-L	X		X	X	X	X	X	X
C-1734	FACT Eating and Swallowing Subscales	X		X	X	X	X	X	X
C-1733	ECOG Acute Esophagitis Scale	X	X	X	X	X	X	X	X
C-1736	Difficulty Swallowing	X	X	X	X	X	X	X	X
C-458	HADS	X		X	X	X	X	X	X
C-903	EQ-5D	X		X	X	X	X	X	X
C-616	Subjective Significance Questionnaire			X	X	X	X	X	X
C-419	QOL Assessment Form	X		X	X	X	X	X	X
C-1735	Treatment Inconvenience			X	X	X			
C-187	Sociodemographic Characteristics	X							

* The assessment should be done at 3, 5, 7, 12, 26 or 52 weeks after the start of radiation therapy. The assessment number entered on the forms should be the same as the week number of the assessment.

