8.0 TREATMENT PLAN

Patients registered to CALGB 30610 prior to the start of cycle 1 protocol treatment will start therapy within 7 days of registration.

Questions regarding treatment should be directed to the Alliance Study Chair.

Protocol therapy will consist of 4 cycles of cisplatin and etoposide or carboplatin and etoposide chemotherapy administered every 21 days. Thoracic radiotherapy will begin either on the first day of the first cycle of chemotherapy OR on the first day of the second cycle of chemotherapy.

Patients may be registered to CALGB 30610 following one cycle of chemotherapy. Patients must receive the second cycle of therapy following registration, on day 22-24, so that the patient adheres to a 3-week treatment cycle. Patients not able to be treated within 3 days of day 22 should not be registered to CALGB 30610. For patients registered to CALGB 30610 after 1 cycle of chemotherapy, the thoracic radiotherapy must begin with the second cycle of chemotherapy (the first cycle of protocol chemotherapy after the patient was registered). Additionally, the cycle of chemotherapy given prior to registration will be considered “cycle 1.” Therefore, patients registered following 1 cycle of chemotherapy will receive three cycles of therapy after registration.

The original design was a randomized phase III trial including two experimental treatment arms (70 Gy once daily radiotherapy and 61.2 Gy concomitant boost radiotherapy) and a standard treatment arm (45 Gy twice daily radiotherapy). An interim analysis, conducted after accrual of a pre-determined number of patients, selected one experimental arm based upon a comparison of treatment related toxicity. The most toxic experimental arm, which was Arm C, was discontinued, and the trial now compares standard therapy to the selected experimental regimen.

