8.2.9 Prophylactic Cranial Irradiation

- Prophylactic cranial irradiation (PCI) should be offered to all patients with a complete tumor response (CR) or near complete response (very good PR) with only residual chest abnormalities of indeterminate nature following completion of combined modality therapy. This will be determined based on the re-staging studies obtained following all four cycles of chemotherapy and thoracic irradiation. PCI should start approximately 3-6 weeks following the final cycle of chemotherapy. No concurrent chemotherapy is given with PCI. For patients with a response to therapy that is less than CR or very good PR, the use of PCI is at the investigator’s discretion.
- Treatment should be delivered with megavoltage radiation.
- The dose and fractionation scheme for PCI is 2500 cGy given in 250 cGy fractions. An RT-2 Form must be completed indicating the start and end date of treatment, fraction dose, number of fractions and total dose. This form should be mailed or faxed to QARC at the address in [section 8.2.8](#).
- The treatment field should encompass the entire cranial contents. The base of the field will extend from the supraorbital ridge, the lateral canthus of the orbit, through the tip of the mastoid process, which is 1.5-2 cm below the external auditory meatus, back to the C1-C2 vertebral interspace.

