In the quality of life companion, patients will be assessed by multiple HRQOL (Health-related quality of life) scales at baseline, 3, 5, 7, 12, 26 and 52 weeks (see [Table 1](#) for details). Investigators are interested in evaluating the change of quality of life assessments from baseline to multiple time points during and after treatment and comparing the differences of such changes between treatment regimens. It is expected that patients in arm 1 (45 Gy) experience worse physical and functional well being, worse esophagitis than those in the remaining study arm (arm 2 or 3), and that patients in arm 2 (70 Gy) experience worse treatment inconvenience than those in arm 1 (45 Gy) or arm 3 (61.2 Gy). The HRQOL scores changed from baseline to 12 week are of the primary scientific interest. The size of the HRQOL companion is chosen such that one has adequate power to test three sets of scientific hypotheses as shown in Table 2). The companion will register 415 patients (57%) from the 729 patients consenting to the main treatment study. Of the 415 patients, 394 patients are expected to meet the eligibility criteria. Of the 394 patients on the companion study, 188 patients are expected in each of the two remaining study arms and 18 patients are in the discontinued study arm.

Table 2
Quality of Life Assessment

QoL Endpoint Variable	Hypothesis	Measure	Statistical Analysis

Primary Endpoints Physical Well-being, Functional Well-Being, Lung Cancer physical symptoms
 
FACT Esophageal Eating and Swallowing Subscales
	
Hypothesis A: At 12 weeks after the start of XRT, patients in the 45Gy arm will report worse physical symptoms and functioning than those in the high dose daily (70Gy) and concomitant boost RT (61.2 Gy) groups.
	
FACT-L (TOI)
 
FACT Esophageal Eating and Swallowing Subscales
	
Continuous scores/outcomes
 
T test; Analysis of covariance; Linear mixed effect model or general linear model with generalized estimating equations

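### The plan says the primary week-12 quality-of-life endpoints precede prophylactic cranial irradiation, but its own timing does not assure this for patients whose thoracic radiotherapy starts with cycle 2

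*Combined protocol and SAP*

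**What the plan says.** Section 10.2.3 expects most patients to receive PCI and calls its effect on quality-of-life measures unclear. It gives two reasons for not pursuing the matter. In two earlier trials neuropsychological change did not differ between patients with and without PCI. It then adds: "Moreover, the primary Quality of Life endpoints are determined prior to PCI administration". PCI is to be considered only later: "Whether patients received PCI will be noted in the analyses of secondary endpoints that occur in the follow-up period after completion of all therapy".

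The primary time point is set in Section 15.7: "The HRQOL scores changed from baseline to 12 week are of the primary scientific interest". Table 2 there lists the FACT-L TOI and the eating and swallowing subscales as primary and HADS as secondary. The clock is set in Section 6.2: "The assessment should be done at 3, 5, 7, 12, 26 or 52 weeks after the start of radiation therapy".

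PCI runs on another clock. Section 8.2.9 says: "PCI should start approximately 3-6 weeks following the final cycle of chemotherapy". It is offered on a complete or near-complete response and is otherwise left to the investigator.

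Section 5.5 includes this stratum: "Start radiotherapy at the second cycle of protocol chemotherapy, without prior non-protocol chemotherapy". Section 1.2 dates the choice of start time to the September 2009 amendment. Section 5.6 bars from the companion studies only patients registered after a cycle of chemotherapy, so patients in this stratum can join the quality-of-life study. The schedule in Section 10.2.2 still follows a cycle-1 start: "7 weeks after the start of radiation therapy (RT completed for all arms; cycle 3 chemotherapy".

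**The concern.** The statement in Section 10.2.3 carries no condition, yet the two events it orders are counted from different origins. Starting radiotherapy one cycle later moves the week-12 assessment 21 days later relative to chemotherapy, while PCI stays where it was. If PCI has begun by then, the primary scores of some patients are taken during or after cranial irradiation and those of others before it.

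This would matter to the comparison if PCI before week 12 differed between arms. It depends on response, which the trial itself compares between arms, and otherwise on the discretion of investigators who know whether treatment is given once or twice daily. A PCI effect on the scores could then be read as an effect of the thoracic regimen. The analysis of covariance in Section 15.7 names only study arm and baseline factors found significant. It names neither PCI nor radiotherapy start time.

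**Working it through.** **The plan's own figure.** Hypothesis A (Section 15.7) has 150 completers per arm, an effect of 0.397 SD and two-sided alpha 0.0167. Power = Φ(0.397 × √(150/2) − 2.393) = Φ(3.438 − 2.393) = 0.852, or 0.848 with the noncentral t. The stated 85% reproduces and is not in dispute.

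**Timing inputs.** Section 8.0: "Protocol therapy will consist of 4 cycles of cisplatin and etoposide or carboplatin and etoposide chemotherapy administered every 21 days". Section 8.1 puts the last etoposide dose on day 3 of each cycle. Section 8.2.9 gives a PCI start window of about 3 to 6 weeks with no defined anchor.

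**Days, counting day 1 of cycle 1 as day 1, with no delays.**
- Cycle 4: day 1 is 1 + 3 × 21 = 64; last dose is day 66; the 21-day cycle ends on day 84.
- PCI start window: anchor + 21 to anchor + 42.
- Week 12: radiotherapy start + 84, which is 1 + 84 = 85 for a cycle-1 start and 22 + 84 = 106 for a cycle-2 start.

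| Anchor | PCI start window | Cycle-1 start (week 12 = day 85) | Cycle-2 start (week 12 = day 106) |
|---|---|---|---|
| Day 1 of cycle 4 (day 64) | 85-106 | opens the same day | opens 21 days before |
| Last dose (day 66) | 87-108 | opens 2 days after | opens 19 days before |
| End of cycle 4 (day 84) | 105-126 | opens 20 days after | opens 1 day before |

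For cycle-2 starters, the share of the 21-day window lying before week 12 is 21/21, 19/21 (about 90%) or 1/21 (about 5%).

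**The schedule in Section 10.2.2.** It places completion of chemotherapy at week 12. That fits a cycle-1 start with the full fourth cycle counted (day 84). With a cycle-2 start, cycle 4 begins 6 weeks after radiotherapy starts and ends at 9 weeks, so the week-7 form falls in cycle 4 and week 12 comes about 3 weeks after the end of chemotherapy.

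**Possible size, by assumption only.** The documents give no share of cycle-2 starters, no PCI uptake by arm and no PCI effect. The shift in the arm difference is (share starting at cycle 2) × (arm difference in PCI before week 12 among them) × (PCI effect in SD).
- Low: 0.25 × 0.05 × 0.2 = 0.0025 SD.
- High: 0.75 × 0.20 × 0.5 = 0.075 SD.

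Against the design effect of 0.397 SD, a shift that masks the effect would leave power at Φ(0.3945 × √75 − 2.393) = 0.847 (low) or Φ(0.322 × √75 − 2.393) = 0.654 (high). The high figure takes all three assumptions at their upper ends.

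**Power if restricted to cycle-1 starters.** With 25%, 50% or 75% starting at cycle 2, 112, 75 or 37 per arm remain, and power is about 72%, 52% or 25%.

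**The case against.** The strongest reply is that nothing shows PCI clearly preceding week 12. The anchor is undefined, and Section 10.2.2 treats chemotherapy as complete at the end of the fourth 21-day cycle. On that count the window opens one day before the assessment under a rule that is itself approximate, and most PCI would follow. PCI also waits for restaging after all four cycles and thoracic radiotherapy (Section 8.2.9) and for brain imaging (Section 7.0). Chemotherapy delays move PCI later but leave the radiotherapy-anchored visit in place; about 19 to 21 days of accumulated delay removes the overlap even on the early anchors. This stands. It lowers the likely frequency of overlap but does not make the unconditional statement true.

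Second, radiotherapy start time is a stratification factor, so cycle-2 starters should be balanced between arms. PCI use that follows from response can also be regarded as part of the effect of assignment. This stands too: without a difference in PCI uptake or timing, or an interaction with arm, PCI mainly adds variance.

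Third, Section 10.2.3 gives a separate neuropsychological reason, and Section 15.7 plans analyses at weeks 3, 5 and 7, before PCI could start on any of these counts with on-schedule chemotherapy. Those analyses are exploratory. Neither argument supports the timing claim or covers the primary week-12 test.

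A reader might infer that the PCI window definitely opens before week 12 for every cycle-2 starter, or that the primary comparison is biased. The documents support neither: the first needs the day-1 or last-dose anchor for a clear margin, and the second needs differential PCI, on which they give no figures.

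**Conclusion.** The point holds in this form: for patients whose radiotherapy starts with cycle 2, no reading of the plan guarantees that the primary quality-of-life assessment precedes PCI. With chemotherapy on schedule, the start window opens between 21 days and 1 day before week 12, depending on an anchor the protocol leaves open. PCI is noted only for secondary endpoints in later follow-up, so the primary week-12 test does not account for it.

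For cycle-1 starters the stated order is consistent with the timing on every count, but with a margin of only 0 to 2 days on the two earlier anchors. That stratum should not be assumed free of PCI without checking dates.

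Any distortion depends on a between-arm difference in PCI uptake or timing. The illustrative 0.0025 to 0.075 SD rests wholly on assumed inputs. The effect is probably modest, and it concerns the quality-of-life companion, not the survival endpoint. The correction is worth making because the timing claim is one of the plan's two reasons for setting PCI aside.

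**What to change.** 1. Reconcile Sections 8.2.9, 10.2.2 and 10.2.3: state which anchor the quality-of-life timing assumes, correct the assessment schedule for cycle-2 starts, and withdraw the unconditional statement. No change to clinical timing is proposed.
2. Include radiotherapy start time, already a randomisation factor, in the primary week-12 quality-of-life models. This alone would not remove differential PCI within the cycle-2 stratum, so the next two steps are also needed.
3. Use the PCI dates on the RT-2 form to flag week-12 forms completed on or after PCI start, and report their number by arm for the primary endpoints. Do not condition the primary test on PCI, which is a post-baseline event.
4. Prespecify a sensitivity analysis of TOI, eating, swallowing and HADS by radiotherapy start time, centred on cycle-1 starters and with PCI dates checked there too. Label it supportive, given the loss of power shown above.

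The cost is protocol and analysis-plan wording, one tabulation and one extra analysis, from data the protocol already requires. Closure of the companion to accrual in August 2017 does not prevent any of this.
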